2. HYPOTHESIS AND SPECIFIC AIMS

Multiple prospective radiation therapy protocols have evaluated bladder-preserving chemoradiation therapy approach for muscle-invasive bladder cancer (MIBC), with radical cystectomy reserved for radiation failure. Aims of bladder preservation in MIBC are to offer a quality-of-life advantage and avoid potential morbidity or mortality of RC without compromising oncologic outcomes. Because of lack of level-1 evidence, oncologic equivalence of bladder preservation modality treatments compared with RC remains unknown.

2.1 HYPOTHESIS:

We hypothesized that chemoradiation is non-inferior to radical cystectomy for treatment of MIBC.

2.2 SPECIFIC AIMS:

SPECIFIC AIM 1a To determine and quantify quality of life in patients treated with radical cystectomy and chemo radiation therapy

1b To determine and quantify progression free survival and bladder-intact survival in patients treated with radical cystectomy and chemoradiation therapy,

SPECIFIC AIM 2a To evaluate genetic markers predicting response to chemoradiation by performing tissue RNA microarrays.

2b To assess the feasibility of conducting an adequately powered non-inferiority trial of the same design via recruitment rate, patient adherence to both treatment arm, and attrition.

2.3 STUDY DESIGN:

Our study will be a pilot, prospective, single-center, randomized non-inferiority trial comparing chemoradiation therapy to radical cystectomy. Patients diagnosed with muscle invasive bladder cancer after transurethral resection of bladder tumor and are surgical candidates will be randomized to either radical cystectomy (with neoadjuvant chemotherapy if suitable candidate) or chemoradiation.

Both treatment methods are considered “standard of care” recommended by the NCCN Clinical Practice Guidelines (http://www.nccn.org/professionals/physician_gls/pdf/bladder.pdf) in treating muscle invasive bladder cancer.

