3.3 Randomization Procedure

A total of 30 patients will be randomized to either chemoradiation group (n=15) or radical cystectomy (with or without neoadjuvant chemotherapy group, n=15). Permuted block randomization process through sequentially numbered, opaque sealed envelopes will be utilized in assigning participants into either radical cystectomy or chemoradiation group. All subjects will be randomized in blocks of size 2. A randomization list containing sequence numbers and treatment assignments will be prepared by the statistician and used as the sole basis for treatment assignments throughout the study.

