to read and consider and ample opportunity will be given to answer any questions. The participant may decline to participate, decide to participate, or take the consent home to think about participating. A copy of the signed consent form will be provided to each participant.

The potential participant will then be scheduled for a TURBT (transurethral resection of bladder tumor) with the treating urologist, which may also be the study's principal investigator or co-investigator. TURBT is the standard of care which allows the treating urologist to formally assess the extent of disease progression and also to evaluate whether the candidate can be treated with both radical cystectomy and chemoradiation treatment. Potential participant will be approached to store any leftover tissue specimens, not needed for diagnosis, into the "GU Tissue Bank" (IRB HSC20050234H). The tissue collected will be processed per standard of care, and slides or tissue blocks may be accessed later for future use in correlative studies. The leftover specimens may be used for future research studies that may include genetic testing related to bladder cancer. This banking portion is optional and not required to be in the main study. If the participant declines to participate in the optional study, any leftover specimens will be permanently de-identified through the GUTB (05-234H).

The potential participant will then return to the clinic for a routine follow-up visit to review the TURBT results and discuss treatment options with the treating Urologist within 4 weeks post-TURBT. Final eligibility will be determined during the TURBT follow-up visit. If potential participant is eligible for the study, randomization will occur. The following section outlines study procedure during the visit.

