9. DATA COLLECTION & STUDY EVALUATIONS

Medical records will be reviewed prior to “Baseline Study Visit” to confirm study eligibility. After obtaining consent, socio-demographic data will be collected through chart review and interviews. Clinical data that will be collected include but not limited to bladder cancer treatment history, tumor characteristics, stage, laboratory results, medications and co-morbidity.

Study team member or clinic staff will measure height, weight, and vital signs at each specific study time point. Research blood will be drawn at each study time point. Blood and tissue samples may be banked under the optional study (HSC20050234H GU Tissue Bank). For those participants who declined to participate in the optional study, any leftover samples will be permanently de-identified through the GU Tissue Bank (HSC20050234H) honest broker system. At the close of this study, all biological materials collected will be rolled into HSC20050234 GU Tissue Bank.

9.1 Feasibility: We will report recruitment, visit dates, adherence, attrition rates and compliance with randomization for each arm of the study

9.2 Bladder-intact survival: We will report proportion of patients who failed chemoradiation and required salvage cystectomy

9.3 Quality of life: A self-assessment questionnaire using the European Organization for Research and Treatment of Cancer (EORTC) QLQ- C30 and FACT-Bladder will be used for QOL assessment at baseline, 3, 6, 9 and 12 months.⁸

9.4 Progression free survival: This will be measured from the date of finishing chemoradiation or radical cystectomy to the date of first documentation of progression. Progression will be determined using RECIST 1.1 criteria by the treating physician based on radiographic or pathologic evidence of disease progression, or death from disease. Any documented recurrence will be considered progression.⁹ The date of progression will be recorded.

9.5 Candidate gene expression analysis: For the participants who have consented to be part of the optional study (“GU Tissue Bank HSC20050234H), a microarray analysis will be performed on all bladder tumor specimens using Agilent Technologies (Agilent SurePrint G3 Human Gene Expression 8x60K v2) Microarray. Goal is to study the landscape of 50 important candidate genes, which are involved in bladder cancer (for example-BRAF, KRAS, EGFR, FGFR).

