Categorical outcomes will be summarized with frequencies and percentages. Continuously distributed outcomes will be summarized with the sample size, mean, standard deviation, median, minimum and maximum. A consort diagram giving the number patients screened, the number of screen failures, the number randomized, the number lost to follow-up by reason, and the number completing the study by treatment arm will be created. In Aim 1a we will test the hypothesis that chemoradiation therapy is non-inferior to radical cystectomy with regard to change in quality of life at 36 months relative to baseline. In Aim 1b, we will test the hypothesis that chemoradiation is non-inferior to radical cystectomy with regard progression free survival and bladder intact survival. With regard to Aim 1a, assuming the 50% (p_2) of patients randomized to radical cystectomy and 60% (p_1) of patients randomized to chemoradiation will experience improvement in quality of life at 3 years relative to baseline and a 5% margin (Δ) of non-inferiority, this study would require $n=171$ subjects per group to attain 80% power for testing $H_0: p_1 - p_2 \leq \Delta$ versus $H_1: p_1 - p_2 > \Delta$ with $\alpha=5\%$. The non-inferiority of chemoradiation compared with radical cystectomy with regard to changes in quality of life (Aim 1a) will be assessed with Fisher's exact test. Progression free and bladder-intact survival (Aim 1b) will be summarized by treatment arm with Kaplan-Meier curves and supporting tabulations and non-inferiority will be assessed with a logrank test. The significance of treatment arm differences with regard to biomarkers (Aim 2a) will be assessed with t-tests or Wilcoxon tests. Pairwise correlations between biomarkers will be displayed overall and by treatment arm. Logistic regression will be used to find a best linear predictor of treatment arm in terms of multiple biomarkers. Biomarkers may be log transformed prior to analysis. Feasibility (Aim 2b) will be assessed with a new power and sample size calculation. If the logistic regression model fails in Aim 2a, random forests will be attempted. If the logrank test fails in Aim 1b, Fisher's exact test will be used. R (v3+, Vienna, Austria) or SAS (SAS Institute, Cary, North Carolina) software will be used throughout.

REFERENCES

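### Aim 2a seeks markers of response to chemoradiation, but Section 11 tests and models the randomised arm, with no error control or validation across 50 genes

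*Combined protocol and SAP*

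**What the plan says.** Section 2.2 states Aim 2a as "To evaluate genetic markers predicting response to chemoradiation by performing tissue RNA microarrays". The Background (Section 1) describes the same goal: a search for molecular differences between responders and non-responders to chemoradiation, with cystectomy as a reference.

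Section 9.5 sets the scope: "Goal is to study the landscape of 50 important candidate genes". Arrays are run only "For the participants who have consented to be part of the optional study", and Section 4.1 says of the tissue bank: "This banking portion is optional and not required to be in the main study". Section 3.3 fixes the ceiling: "A total of 30 patients will be randomized to either chemoradiation group (n=15) or radical cystectomy", also 15 patients.

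Section 11 gives the analysis: "The significance of treatment arm differences with regard to biomarkers (Aim 2a) will be assessed with t-tests or Wilcoxon tests". It continues: "Logistic regression will be used to find a best linear predictor of treatment arm in terms of multiple biomarkers". There is a fallback: "If the logistic regression model fails in Aim 2a, random forests will be attempted". Failure of the model is not defined.

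The supplied text gives no significance level for these tests, no multiplicity adjustment, no rule for choosing genes, no penalty and no validation step. It does not label the gene results as exploratory.

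**The concern.** The aim and the analysis have different outcomes. The aim concerns who responds to chemoradiation; the analysis concerns which arm a patient was allocated to. Under Sections 4.1 and 4.2, TURBT comes first and randomisation follows at the baseline visit. Expression in TURBT tissue therefore cannot depend on the arm. A significant gene in that comparison is a chance imbalance, and a model that predicts arm well has fitted the envelope draw.

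The lack of error control makes this worse, and would still matter if the outcome were corrected. With 50 genes and few patients, some nominally significant genes and a well-fitting multi-marker model can arise from noise, and no planned step would show it. At stake is whether Aim 2a answers its question at all, and whether a reader could tell signal from noise in the results.

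**Working it through.** **No planned figure to reproduce.** The plan gives no error rate, power or sample size for Aim 2a. Its only formal sample size, 171 per group, is for quality of life (Aim 1a) and does not bear on this point.

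**Step 1: aim against analysis.**

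| Item | Section | Content |
|---|---|---|
| Question | 1, 2.2 | Response to chemoradiation |
| Tissue timing | 4.1, 4.2 | TURBT before randomisation |
| Response data | 6 | Biopsy and cytology after induction, chemoradiation arm |
| Tests and model | 11 | Treatment arm |

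For TURBT tissue the null hypothesis of no arm difference is true by design. Banking consent is also sought before randomisation, so this holds in the consenting subset. Response does not enter the Section 11 analysis, although Section 6 records it.

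**Step 2: false positives across 50 genes.** Inputs: 50 genes (Section 9.5), and a per-gene significance level that is an assumption, because Section 11 states 5% only for Aim 1a. Testing each gene separately is inferred from Sections 9.5 and 11 together.

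- Expected false positives with no true differences = 50 × level. This mean does not depend on correlation between genes.
- Chance of at least one, for independent genes = 1 − (1 − level)^50.

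| Assumed level | Expected | At least one (independent) |
|---|---|---|
| 1% | 0.5 | 39.5% |
| 2.5% | 1.25 | 71.8% |
| 5% | 2.5 | 92.3% |
| 10% | 5.0 | 99.5% |

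Simulation at 5% (15 versus 15, equally correlated genes, 6,000 runs per setting) gives a chance of at least one of about 81%, 63% and 32% at correlations of 0.3, 0.5 and 0.8. The mean stays at about 2.5.

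**Step 3: the multi-marker model.** With 30 patients, an intercept and 29 genes give 30 coefficients, enough to separate any two groups when the expression values are continuous. In simulated pure noise at 15 versus 15 (500 runs per setting), an unpenalised model separated the arms perfectly in 100% of runs with 29 or 50 genes and in 48% with 14. Choosing the best 10 of 50 noise genes by t-test gave perfect separation in 71% of runs; the best 8, in 38%.

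**Step 4: what adjustment costs.**

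- Bonferroni level: 0.05/50 = 0.001. Under independence, the chance of any false positive is 1 − 0.999^50 = 4.9%.
- At 15 versus 15, the difference detectable with 80% power rises from 1.06 SD to 1.67 SD. Power for a 1 SD difference falls from 75% to 21%.
- For response within the chemoradiation arm, assume 10 responders and 5 non-responders (the documents give no split). The detectable difference rises from 1.66 SD to 2.86 SD.
- With the same split, Benjamini-Hochberg at 10%, independent genes and 5 of 50 truly different by 1 SD, simulated power per true gene is about 8%, against about 40% unadjusted.

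**The case against.** The fairest defence is that this is a pilot. The Background calls the gene work a search and speaks of selecting patients by markers only conditionally. Aim 2b judges feasibility on recruitment, adherence and attrition, and no decision rule uses a gene. A reader might infer that chance markers will be carried into the larger trial; no passage says so. This defence lowers the stakes, but Section 11 still assesses significance and does so on the wrong outcome.

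A second defence is that cystectomy is named as a reference, so an arm comparison may be intended. Using it as a reference for a predictive marker would mean asking whether the marker's relation to outcome differs by arm. Comparing marker levels between arms does not ask that.

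A third is that Section 9.5 covers all bladder tumor specimens and the Section 9.8 table lists blood as well as tissue. In samples taken after treatment begins, arm differences could be real. They would reflect exposure to treatment and would not identify responders, so the mismatch with the aim remains. The argument that every difference is chance applies only to material collected before randomisation.

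Finally, Section 11 refers to multiple biomarkers without saying that all 50 enter the model or that it is unpenalised. Perfect separation is therefore conditional on how many genes are used and how they are chosen. That qualification stands.

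**Conclusion.** The point holds, with the choice of outcome as its main part. As written, the Section 11 analysis cannot answer Aim 2a. For pre-randomisation TURBT tissue, every significant arm difference is a false positive, and this conclusion needs no assumption about significance level or correlation.

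Missing error control and validation is a real but secondary fault. Its size is 2.5 expected false positives if all 50 genes are tested at 5% with no true differences, with a range of 0.5 to 5 for levels of 1% to 10%. The 92% chance of at least one needs independent genes and should not be quoted alone.

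Two stronger readings are tempting and do not hold. The small sample does not itself create false positives: a valid t-test or Wilcoxon test keeps its error rate, and what is lost is power. The pairwise gene correlations do not add to the error count either, because Section 11 only displays them.

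The absence of safeguards is judged on the supplied text. The study synopsis mentioned in Section 8.2 was not available.

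**What to change.** Revise the Aim 2a text in Section 11, before any gene data are analysed, as follows.

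1. Make post-induction response, as recorded under Section 6, the outcome for the tests and any model. Restrict the analysis to the chemoradiation arm and use pre-treatment TURBT tissue. State how patients with no response evaluation are handled.
2. List the 50 genes. For each, report the effect size with its confidence interval and a p-value adjusted for the false discovery rate across all 50.
3. If a multi-marker model is fitted, use a penalised one and report cross-validated performance, with gene selection repeated inside each fold. Apply the same validation to random forests, and define what counts as failure of the logistic model.
4. Label Aim 2a hypothesis-generating.

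This needs no extra patients, visits or assays, only protocol wording and routine analysis. The statistical cost is substantial. At most 15 patients contribute, fewer if banking is declined. Adjusted p-values will rarely be significant, and cross-validated estimates will be unstable with so few non-responders. The usable product is a set of effect estimates with honest uncertainty.

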10. DATA AND SAFETY MONITORING OVERSIGHT

A Data and Safety Monitoring Plan (DSMP) is required for all an individual protocols conducted at CTRC. All protocols conducted at CTRC are covered under the auspices of the CTRC Institutional Data Safety Monitoring Plan. The scoring algorithm for each questionnaire will be included in the data entry system.

The CTRC Institutional DSMP global policies provide individual trials with:

- institutional policies and procedures for institutional data safety and monitoring,
- an institutional guide to follow,
- monitoring of protocol accrual by the CTRC Protocol Review Committee,
- review of study forms and orders by the Forms Committee,
- tools for monitoring safety events,
- monitoring of UPIRSO's by the Director of Quality Assurance and DSMC,
- determining level of risk (Priority of Audit Level Score – PALS) ,
- oversight by the Data Safety Monitoring Committee (DSMC), and
- verification of protocol adherence via annual audit for all Investigator Initiated Studies by the CTRC Quality Assurance Division.

10.1 Monitoring Safety:

The Principal Investigator will perform primary assessment of adverse events, adverse event trends and treatment effects on this study. The PI will conduct independent quarterly review and report findings to the CTRC Data Safety Monitoring Committee (DSMC) and the UTHSCSA IRB.

Baseline events and adverse events will be captured using the CTRC Master Adverse Events Document for each patient using CTCAE V.4.03 for the grading and attribution of adverse events. Usage of the CTRC Master Adverse Events Document centrally documents:

- the event and grades, severity, and the seriousness of it,
- if the event was a change from baseline,
- the relationship between the event and study intervention
- if the event was part of the normal disease process, and
- what actions were taken as a result of the event.

10.2 Safety Definitions:

For this study, the following safety definitions will be applicable:

Adverse Event Definition: An adverse event (AE) is defined as any untoward or unfavorable medical occurrence in a human subject, including any abnormal sign (for example, abnormal physical exam or laboratory finding), symptom, or disease, temporally associated with the subject's participation in the research, whether or not considered related to the subject's participation in the research. For this study, all adverse events will be documented starting with the date of study enrollment and ending 30 days after the "12 months post-treatment study visit".

Serious Adverse Event Definition: is any adverse event that:

1. results in death;

2. is life-threatening (places the subject at immediate risk of death from the event as it occurred);
3. results in inpatient hospitalization or prolongation of existing hospitalization;
4. results in a persistent or significant disability/incapacity;
5. results in a congenital anomaly/birth defect; or
6. based upon appropriate medical judgment, may jeopardize the subject's health and may require medical or surgical intervention to prevent one of the other outcomes listed in this definition

Unanticipated Problems Involving Risks to Subjects or Others Definition: Unanticipated problem involving risk to subjects or others includes any incident, experience or outcome that meets all of the following criteria:

- A. unexpected (in terms of nature, severity, or frequency) given (a) the research procedures that are described in the protocol-related documents, such as the IRB-approved research protocol and informed consent document; and (b) the characteristics of the subject population being studied (note: the unfounded classification of a serious adverse event as "anticipated" constitutes serious non-compliance);
- B. definitely related or probably related to participation in the research; and
- C. suggests that the research places subjects or others at a greater risk of harm (including physical, psychological, economic, or social harm) than was previously known or recognized

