4.3. Required Evaluations/Management (baseline prior to initiation of any protocol treatment)

- a) Cystoscopic evaluation by the participating urologic surgeon no more than 6 weeks prior to registration will include bimanual examination under anesthesia, as thorough as possible, a transurethral resection of the bladder tumor. Patients referred from an outside hospital with a muscularis propria-invading bladder tumor will be re-resected by the participating urologist.
- b) Radiologic evaluation including chest CT, abdominal and pelvic CT and bone scan no more than 6 weeks prior to start of treatment.
- c) Comprehensive metabolic panel (CMP) obtained no more than 4-6 weeks prior to registration

5. Randomization

5.1 Radical Cystectomy Arm- Those randomized to “Radical Cystectomy” will be scheduled for surgery. In brief, radical cystectomy is the removal of the entire bladder, nearby lymph nodes (lymphadenectomy), part of the urethra, and nearby organs that may contain cancer cells. In men the prostate, the seminal vesicles, and part of the vas deferens are also removed. In women the cervix, the uterus, the ovaries, the fallopian tubes, and part of the vagina are also removed. Participants in this group may also undergo neoadjuvant chemotherapy prior to the surgery as is the current standard of care. The decision for specific chemotherapy regimen is based on medical oncologist’s evaluation. All AE occurring during the study period will be assessed and attribution assigned.

The surgical approach, robotic versus open, is determined by patient and surgeon mutual preference. All urinary diversions will be done via an open incision and the mode of diversion, whether intracorporeal or extracorporeal (orthotopic neobladder, continent cutaneous diversion or ileal conduit) will be selected by mutual agreement of the surgeon and patient, as is customarily done. The extent of the lymph node dissection will be determined by the surgeon but at minimum will include the external iliac, obturator, and hypogastric regions.

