5.3 DRUG THERAPY

Medical Oncologist will determine the chemotherapy regimen concurrently used with radiation as a radiation sensitizer. The following is a list of chemotherapeutic drugs that could be used per NCCN guideline:

Cisplatin

Cisplatin and 5-FU

5-FU and Mitomycin

Cisplatin and Paclitaxel

Low dose gemcitabine

All AE occur during the study period will be assessed and attribution assigned.

6. Post-Induction Response Evaluation (for Chemoradiation Arm only)

Following the completion of induction chemoradiotherapy and the evaluation of response all patients must be re-registered via cystoscopy and biopsy. At this time, the response results (biopsy results and cytology results) and the second phase of the treatment (i.e. radical cystectomy for tumor response $T \geq 1$ or consolidation chemoradiotherapy for tumor response T0, Ta, and Tcis) will be recorded and a new data collection calendar generated. Details regarding “Radical Cystectomy” can be found at Section 5.1. Details regarding “Consolidation Chemoradiotherapy” can be found at Section 5.2.2.

The following information will be supplied:

- original case number
- results of evaluation and pathologic T stage
- treatment start date (radical cystectomy or consolidation chemoradiotherapy)

The treatment option registered and the new data collection calendar will be based on the parameters specified by the protocol. If the investigator or the patient deviates from the protocol specified treatment, documentation of this and data submission as outlined in our study Standard operating procedure.

Patients who have developed distant metastases during the induction phase of treatment and who will not continue therapy will remain on the original calendar schedule for continued follow up only.

After completing either radical cystectomy or consolidation chemoradiotherapy, all response results to the second phase of treatment (i.e., either pathologic staging from the radical cystectomy or cystoscopic re-evaluation performed following completion of consolidation chemoradiotherapy) will be promptly submitted to Data Management.

7. 1 Post-Treatment Study Visits at 3, 6, 9, 12, 18, 24, 30, and 36 month \pm 1 month

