Post-treatment study visits will occur every three months (\pm 1 month) up to one year and every six months (\pm 1 month) thereafter up to two years (i.e. Months 18, 24, 30, and 36). These study visits will be scheduled during the same time as the participant's routine visit (i.e. standard of care) whenever possible. If not, study team member will work with participant on a time that is convenient. An imaging study either a CT abdomen and pelvis or MRI of abdomen and pelvis will be done as standard of care prior to the routine clinic visit. The treating physician will assess AE and assign attribution. Research study team member will coordinate with the participant to meet either before or after the routine clinic visit. Participants will be asked to complete study questionnaires. The questionnaires may also be mailed and/or emailed back to the study team if they cannot be completed within the allotted study time. And those randomized to "chemoradiation Group" will also undergo routine cystoscopy during these follow-up visits (SOC).

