8. STUDY CALENDAR

8.1 RADICAL CYSTECTOMY ARM

	Initial visit	Pre-Treatment (tx) TURBT	Baseline	Treatment Period: Radical Cystectomy	Post-tx 3 mon f/u ± 1 mon	Post-tx 6 mon f/u ± 1 mon	Post-tx 9 mon f/u ± 1 mon	Post-tx 12 mon f/u ± 1 mon	Post-tx 18 mon f/u ± 1 mon	Post-tx 24 mon f/u ± 1 mon	Post-tx 30 mon f/u ± 1 mon	Post-tx 36 mon f/u ± 1 mon (end of study visit)		
Study eligibility	X		X											
Informed consent	X													
Assessment of AE						X	X	X	X	X	X	X	X	X
SOC Image studies (X-Ray, CT, and/or MRI)			X			X	X	X	X	X	X	X	X	X
Research blood sample			X			X	X	X	X	X	X	X	X	X
Ht, Wt, and Vitals [#]			X			X	X	X	X	X	X	X	X	X
Research Study Questionnaires			X			X	X	X	X	X*	X*	X*	X*	X*

Note:

SOC = Standard of Care

[#] information may be extracted from EMR

*Research study questionnaire may be emailed or mailed per patient's stated preference

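### Section 10.2 ends adverse-event documentation at about month 13, contradicting the visit schedule, both calendars and the treatment-arm sections, which call for adverse-event assessment through the study period, to month 36

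*Combined protocol and SAP*

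**What the plan says.** Section 10.2 (Safety Definitions) is the only place that gives a start and an end for AE documentation: "all adverse events will be documented starting with the date of study enrollment and ending 30 days after the" 12-month post-treatment visit. The same section defines an SAE as an AE that meets one of six listed criteria.

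Other sections point to a longer period:

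- The heading of Section 7.1 reads "Post-Treatment Study Visits at 3, 6, 9, 12, 18, 24, 30, and 36 month", and its text says of these visits: "The treating physician will assess AE and assign attribution". No month-12 limit is attached.
- Section 5.1 (cystectomy arm) says: "All AE occurring during the study period will be assessed and attribution assigned". Section 5.3 (drug therapy) says nearly the same for the chemoradiation arm.
- Section 8.1 labels its last column "Post-tx 36 mon f/u ± 1 mon (end of study visit"), and its row "Assessment of AE" is marked through to that column. Section 8.2 has the same row, marked in the same way.

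The end of follow-up is itself not cleanly stated. Section 7.1 describes six-monthly visits "thereafter up to two years (i.e. Months 18, 24, 30, and 36"), which names two years but lists visits to three. The month-36 column in Section 8.2 carries two question marks after its end-of-study label.

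**The concern.** Staff who treat Section 10.2 as the operative rule may stop recording AEs about a month after the 12-month visit, although the treating physician goes on assessing them for roughly two more years. Staff who follow Section 7.1 and the calendars would record them to month 36. Both readings comply with some part of the protocol.

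Four things are at stake.

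- Safety is among the captured items in Section 9.8, and Section 1 says the pilot is to provide feasibility data for a larger trial of efficacy and safety. The radiation AE list in Section 5.2.8 names chronic as well as acute bladder bleeding, so the protocol itself expects some toxicity that is not confined to the treatment period.
- Because SAEs are defined through AEs, the end date can be read to apply to SAEs as well.
- The monthly investigator review in Section 10.3 works from the Master Adverse Events Document, and the quarterly committee report and the trigger at three occurrences of one event rest on the same recorded events. An event left undocumented may not reach these checks.
- Section 11 tests change in quality of life at 36 months. Benefit at 36 months would stand beside toxicity recorded for about 13.

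**Working it through.** The plan states no figure for this point, so there is none to reproduce. The check is calendar arithmetic and a comparison of sections.

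**Inputs.** AE window: ends 30 days after the 12-month visit (Section 10.2). Visits: months 3, 6, 9, 12, 18, 24, 30 and 36, each ± 1 month (Section 7.1). End of study: month 36 (Section 8.1). One month = 365.25/12 = 30.44 days, so 30 days = 30/30.44 = 0.99 month.

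**End of window and uncovered time.** End = month of the 12-month visit + 0.99. Uncovered = 36 − end. Share = uncovered/36.

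| 12-month visit held at | Window ends | Uncovered to month 36 | Share of 36 months |
|---|---|---|---|
| month 11 | 11.99 | 24.01 | 66.7% |
| month 12 | 12.99 | 23.01 | 63.9% |
| month 13 | 13.99 | 22.01 | 61.2% |

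**Visits outside the window.** The earliest possible 18-month visit is at month 18 − 1 = 17, and the latest possible end of window is month 13.99. Visits 18, 24, 30 and 36 therefore fall outside whatever the visit timing: 4 of 8.

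**If follow-up ended at two years.** Taking the two-year wording in Section 7.1 literally, 24 − 12.99 = 11.01 months (11.01/24 = 46%) and visits 18 and 24 are still outside. The contradiction does not depend on which horizon is meant.

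**Calendars.** The tables are broken in the available text. Each AE row shows nine consecutive marks running to the last column, against eight post-treatment visits. Whichever column takes the extra mark, the run includes months 18 to 36.

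**Sections side by side.**

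| Section | What it requires | End point |
|---|---|---|
| 10.2 | AE documentation | 12-month visit + 30 days |
| 7.1 | AE assessment and attribution at post-treatment visits | none stated; visits to month 36 |
| 8.1, 8.2 | AE assessment | last visit, month 36 |
| 5.1, 5.3 | all AEs assessed and attributed | study period |
| 10.1 | AEs captured on the master document | none stated |

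Only Section 10.2 stops at month 12 plus 30 days, and only Section 10.2 gives explicit dates.

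**The case against.** The strongest reply is that late AEs are not in fact lost. Section 7.1, both calendars and Sections 5.1 and 5.3 require AE assessment, Section 10.1 captures AEs with no time limit, and Section 10.2 does not forbid later recording. Unanticipated problems have no 12-month limit in their definition, and progression, death from disease and salvage cystectomy are collected separately under Section 9. This stands as far as it goes, and it is why the point is a contradiction and not an absence of late safety follow-up. It does not remove the problem: assessing an event is not the same as documenting it, and the only dated rule for documentation stops early. The separate captures do not replace AE records for expected late toxicity.

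Several stronger readings are tempting and are not supported:

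- *That the sponsor chose to truncate safety collection.* No rationale is given and the other sections point the other way. Sections 9.3 and 9.6 also stop at month 12, which suggests a leftover from a shorter schedule but does not prove it.
- *That about 64% of toxicity would be missed.* The 64% is a share of calendar time. The documents give no AE rates.
- *That sites would apply different rules.* Section 2.3 describes a single-center trial. Treatment may be given elsewhere, but follow-up visits return to the study's facilities (Section 4).
- *That all the listed radiation effects are late ones.* Section 5.2.8 calls only bleeding chronic. It gives no timing for fistula or ureteral obstruction.
- *That a planned safety comparison is invalidated.* Section 11 specifies no between-arm AE test, and Section 9.8 lists safety among study processes. The loss is to the descriptive record.

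**Conclusion.** The point holds as an internal contradiction. Section 10.2 closes AE documentation at about month 13 (12 to 14 with the visit window). Following it leaves about 23 of 36 post-treatment months (22 to 24, or 61% to 67%) and four of eight visits without required AE documentation, and it leaves the status of SAEs after that date open. The figures assume that follow-up ends at month 36, as the visit list and the cystectomy calendar say; on a two-year horizon the gap is about 11 of 24 months and two visits. How many events this would affect, and whether the arms would be affected unequally, cannot be computed from the documents. It is worth correcting even in a pilot with 15 patients per arm, because events not recorded at the time are harder to recover later and the assessments that would supply them are already scheduled.

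**What to change.** Amend Section 10.2 so that AE and SAE documentation runs from enrollment to the end-of-study visit (month 36 in the visit list and calendars), or to 30 days after it, and say explicitly that the period applies to SAEs. In the same amendment, define the study period that Sections 5.1 and 5.3 refer to, correct the two-year wording in Section 7.1 so that it agrees with the months listed there, and remove the question marks from the month-36 column in Section 8.2. Settling the follow-up horizon comes first, since the AE end date depends on it, so the change is more than one line.

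No visits or assessments are added. The cost is data entry for AEs in months 13 to 36, and over the same period continued SAE reporting, monthly investigator review, quarterly reports to the safety committee and source verification. In a trial of 30 patients this is a small burden.
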